Criminal Justice Records Review	Objective		X
Targeted Mechanisms of Action			
Valued Living Questionnaire 	Self-report	X	X
Multidimensional Scale of Perceived Social Support 	Self-report	X	X
NIH Toolbox Instrumental Support Fixed Form Age 18+ v2.0 	Self-report	X	X
Treatment History Interview-4 	Interview	X	X
Brief Adherence Rating Scale 	Interview	X	X
Medical Records Review	Objective	X	X
Participant Satisfaction			
Client Satisfaction Questionnaire-8 	Self-report		6 mo only
End of Intervention Questionnaire	Self-report		6 mo only
Exit Interview	Interview		6 mo only
COVID-19			
Coronavirus Impact Scale			6 mo only

**Please note:** The post-release enrollment assessments are the same as the pre-release enrollment assessments. However, the schedule of assessments is slightly different. Post-release enrolled participants will not complete a pre-release assessment. Items specific to the pre-release assessment that are not already included in the baseline assessment are added to the baseline for post-release enrolled participants.

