### **3.b.9. Data analysis.**

For this pilot effectiveness study, assessment of feasibility and acceptability of the intervention and research procedures is the primary goal. Nonetheless, pilot data can be used to demonstrate whether the effects of treatment look promising across a set of outcome variables, to begin to examine distribution of outcome variables to inform future analytic strategies, and to suggest, in concert with results from larger scale clinical trials in related fields, the range of effect sizes that would be reasonable to expect in a future trial.

Study Feasibility and Treatment Feasibility/Acceptability. One of the primary goals of a pilot study is to demonstrate the feasibility of the proposed treatment and of the study and recruitment methods. As a result, we will assess the feasibility of the research procedures by examining study recruitment and refusal rates, participants' willingness to be randomized, follow-up rates, reliability and range of responses to study questionnaires, and success of the interventionist training program. We will assess the feasibility and acceptability of CARE by examining rates of treatment attendance, rates of treatment completion (attending at least 3 of the 4 initial sessions and completing 6 out of the 11 scheduled post-release telephone calls) and drop-out, and reports on the End of Intervention Questionnaire. We will also examine reasons for termination for consistent patterns. We will examine the acceptability of both CARE and E-TAU using data from CSQ-8 treatment satisfaction and end of intervention questionnaires and detailed exit interviews.

Primary Outcomes: Using multilevel modeling of group by time, we will calculate the effect size and 95% CI for percent time symptomatic using the LIFE, with percent time symptomatic in the 90 days prior to study enrollment as a covariate. We will calculate similar exploratory tests for symptom severity using the QIDS and ASRM total scores, with baseline scores as covariates.

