Secondary Outcomes: Using multilevel modeling of group by time, we will calculate the effect sizes and 95% CIs for: (1) percent time suicidal, as assessed by the LIFE, (2) alcohol and drug use severity using the AUDIT and DUDIT, respectively, and (3) overall functioning, employment stability, and housing stability, using the SF-12, JSI, and HSS, respectively. All assessments will use baseline scores, including percent time suicidal in the 90 days prior to study enrollment, as covariates. Potential group differences in rate of re-arrest will be calculated using simple chi-square analysis.

Target engagement/mechanisms of action. In this study, we will explore potential group differences in CARE's purported mechanisms of action. To that end, we will rely upon multilevel modeling of group

by time to calculate effect sizes and 95% CIs for change in VLQ, NIH Toolbox Instrumental Support, MSPSS, THI, and BARS scores across study time points. Across the four assessment time points, we will also evaluate associations between change in these intermediary constructs and primary/secondary outcome measures, using multilevel models.

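### The Aim 5 mechanism models specify neither a baseline covariate nor a common baseline mean, so a default fit would give wider confidence intervals than the data allow

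*Combined protocol and SAP*

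**What the plan says.** Aim 5 (Section 3a) asks for 95% confidence intervals around CARE versus TAU differences in the proposed mechanisms. Section 3.b.9 treats baseline differently across its paragraphs:

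- **Primary outcome:** percent time symptomatic is modelled "with percent time symptomatic in the 90 days prior to study enrollment as a covariate".
- **Symptom severity:** exploratory models for "symptom severity using the QIDS and ASRM total scores, with baseline scores as covariates".
- **Secondary outcomes:** "All assessments will use baseline scores, including percent time suicidal in the 90 days prior to study enrollment, as covariates".
- **Mechanisms:** "To that end, we will rely upon multilevel modeling of group" by time, to obtain "effect sizes and 95% CIs for change in VLQ, NIH Toolbox Instrumental Support, MSPSS, THI, and BARS scores across study time points". No covariate is named, and nothing is said about baseline means.

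The next sentence of the mechanism paragraph begins "Across the four assessment time points, we will also evaluate associations between change in these intermediary constructs". Under Section 3.b.6 the count of four is reached only by including baseline: baseline, pre-release, 1 month and 6 months. Post-release enrollees have three visits.

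In Table 2 (Section 3.b.8) the rows for the VLQ, the "Multidimensional Scale of Perceived Social Support", the NIH Toolbox Instrumental Support form, the THI-4 and the BARS are all marked at baseline.

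**The concern.** The data needed for baseline adjustment will be collected, and the plan uses such adjustment elsewhere. The mechanism paragraph leaves it out and makes change over time the target.

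If baseline is a response in a group-by-time model and each arm has its own baseline mean, the contrast at a follow-up visit is the between-arm difference in change from baseline. That contrast carries the full noise of the baseline measurement. Adjusting for baseline, or giving the arms one baseline mean (which randomization justifies), removes part of that noise.

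The interval itself is what Aim 5 delivers, and Section 3.b.9 intends pilot estimates to suggest plausible effect sizes for a later trial. With 40 participants, precision that costs nothing is worth having.

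**Working it through.** The documents give no interval width, standard deviation or correlation for these measures, so there is no planned figure to reproduce. The check is in SD units.

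**Inputs from the documents:** 40 randomized (Aim 3), 1:1 allocation (Section 3.b.6), so n = 20 per arm; 95% intervals (Aim 5), taken as two-sided.

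**Assumptions:** continuous, complete scores; equal variances at baseline and follow-up; baseline-to-follow-up correlation rho, varied because the documents do not state it.

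**Formulas for the 95% half-width**

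- Free baseline means (change-score precision): t(38) × sqrt[2(1 − rho) × 2/n]
- Baseline-adjusted: t(37) × sqrt[(1 − rho²) × (2/n) × (1 + 1/(2n − 4))]. The last factor is the expected cost of chance baseline imbalance, 1 + 1/36 at n = 20.

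**Example, rho = 0.5.** Change: 2.024 × sqrt(1.0 × 0.1) = 0.640. Adjusted: 2.026 × sqrt(0.75 × 0.1 × 1.0278) = 0.563. Ratio 0.879, or 12% narrower.

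| rho | Change | Adjusted | Narrower by |
|---|---|---|---|
| 0.3 | 0.757 | 0.620 | 18% |
| 0.5 | 0.640 | 0.563 | 12% |
| 0.7 | 0.496 | 0.464 | 6% |
| 0.9 | 0.286 | 0.283 | 1% |
| 0.95 | 0.202 | 0.203 | no gain |

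For reference, ignoring baseline altogether gives 0.640 at any rho. Below rho = 0.5 the change contrast is therefore less precise than not using the baseline at all.

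**Does this carry over to the multilevel model?** Generalized least squares was applied to the group-by-time model with categorical time and compound symmetry.

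- With free baseline means, the standard error of the last-visit contrast at rho = 0.5 is 0.316 SD, equal to sqrt(0.1), the change-score value.
- With a common baseline mean it is 0.274 SD, equal to sqrt(0.075), the large-sample adjusted value. The ratio is 0.866.
- The ratios are the same with three and with four time points.
- If time enters as a linear slope, the gain is smaller. At rho = 0.5 the ratio is 0.90 with four visits and 0.91 with three, using assumed visit times.

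**Simulation.** With 5,000 trials per rho at 40 participants, the adjusted-to-change width ratios were 0.818, 0.879, 0.934 and 0.989 for rho of 0.3, 0.5, 0.7 and 0.9.

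**Dropout.** At an assumed 16 per arm the formula ratios barely move: 0.822, 0.883 and 0.940 for rho of 0.3, 0.5 and 0.7.

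**The case against.** The strongest reply is that the plan does not commit to the less precise model. It specifies multilevel modelling, the same wording used for the other outcomes, and a common baseline mean is compatible with that wording. If the analyst imposes it, nothing is lost. A reader might infer that computed change scores are the dependent variable, or that the intervals will certainly be too wide. The text says neither. That baseline is among the responses is itself inferred, partly from a count of visits in the sentence on associations. What remains is that no constraint is stated and a default fit leaves baseline means free.

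The secondary-outcomes sentence on baseline covariates could be read as covering Aim 5. Its place inside that paragraph, before the mechanism heading, argues against this. If it was meant to apply, the text would still need correcting, because baseline should not be both a response and a covariate in one model.

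Other points on this side stand:

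- A reader might infer that rho is low because pre-release enrollees move from custody to the community. This is conjecture. It does not fit post-release enrollees, or the pre-release visit, which is normally also in custody.
- Chance baseline imbalance is not a second harm. It is the same loss of variance described another way.
- One ratio may not suit all five measures. Section 3.b.2 expects some participants to receive no treatment, and the documents do not show that the THI gives a continuous score or that the BARS can be scored for someone on no medication.
- The aim is exploratory, with no decision rule attached. At rho = 0.5, half-widths of 0.640 and 0.563 SD are both wide.

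**Conclusion.** The point holds as a gap in specification with a modest, conditional cost in precision. For Aim 5 the plan states neither a baseline covariate nor a common baseline mean. If the models are fitted with free baseline means and categorical time, adjustment would narrow the intervals by about 18%, 12% and 6% at rho of 0.3, 0.5 and 0.7, with almost no gain from 0.9 upward. These figures rest on 20 per arm, continuous scores, equal variances and an assumed rho.

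A reader might go further and infer bias in the mechanism comparisons. The documents do not support that: allocation is randomized, and under randomization both analyses estimate the same difference without bias. This is an improvement to an exploratory aim, not a validity error.

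**What to change.** Add to the mechanism paragraph of Section 3.b.9 a statement that the Aim 5 models will use one of the following, but not both:

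- post-baseline scores as the outcome, with the baseline score as covariate; or
- baseline as a time point, with one baseline mean common to the two arms.

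The two are not interchangeable when a baseline score is missing. The second keeps that participant, while the first drops them unless the score is imputed. In a trial of 40 this may favour the second.

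State also that the CARE minus E-TAU adjusted difference, with its 95% interval, will be reported at 1 and 6 months, and at the pre-release visit for pre-release enrollees only, since post-release enrollees have no such visit.

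The cost is a sentence or two of text. No new data are needed, because all five measures are already scheduled at baseline. The team should confirm how the THI and BARS will be scored for participants with no treatment or no medication at baseline before applying the model to them.

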### **3.b.10. Material inducements.**

We will compensate participants \$40 for each of the three follow-up assessments for pre-release enrolled participants (immediate pre-release, 1 month post-release, 6 months post-release) in the form of a money order or a gift card (if they do not have state or federal identification to cash the money order). For post-release enrolled participants, they will be compensated \$40 for each of their completed assessments (baseline, 1 month follow-up, and 6 month follow-up). In total, participants may receive up to \$120 if they complete all study assessments. Compensation for the pre-release assessment will be mailed to an address of the participant's choosing after it is confirmed that the participant has been released from prison. If a follow-up is completed in jail or prison, we will provide the participant the following options: a) us mailing the compensation once they are released, or b) mailing it to a family member or significant other of their choosing, or c) depositing it into their commissary account at the [REDACTED]

### **3.b.11. Training of research personnel.**

All research personnel will have formal training in research with human subjects (e.g., CITI training, GCP training). [REDACTED] will provide training to and supervise research assistants. RAs will have a bachelor's or master's degree, and will receive training in the informed consent process and their ethical responsibilities when conducting research, with a particular focus on the ethics involved with research in perinatal populations. All interviewers will receive specific training in the assessment instruments to be administered and in all study-related safety protocols. With assistance from study [REDACTED] [REDACTED] will supervise the study therapists.

## **3c. Protection of Human Subjects**

Please see section 3.b.1 for a detailed description of study participants. Special classes. Because the purpose of the application is to develop and evaluate the feasibility and acceptability of CARE in prisoners during the vulnerable period of community re-entry, it is necessary to sample a prison population. Prisoners are an understudied population with complex treatment needs; hence the urgency for more research attending to the mental health concerns of this population. Because the target population for this study is constituted by sentenced prisoners with BD, the Prisoner Checklist for research has been included as an appendix to this application. It is anticipated that, once approved, the [REDACTED] IRB will apply to OHRP for project certification. Incarcerated children 18-21 will be eligible.

### **3.c.1. Inclusion of Women and Minorities**

Because the purpose of this application is to develop and pilot an intervention for prisoners with bipolar disorder (BD) around the period of community re-entry, the study population will consist of sentenced male and female inmates who meet criteria for BD. The study sample will also include participating family members/significant others (SOs). Equal numbers of male and female prisoners and SOs will be recruited.

Extant data from prisoners at participating facilities in [REDACTED] have been used to estimate the racial and ethnic distribution of the 104 participants (52 prisoners; 52 SOs) in the open and randomized trials. For females, the overall racial distribution will be approximately 66% White, 17% African American, 2% Asian, 4% American Indian or Alaska Native, and 11% other. The overall ethnic distribution for women will be approximately 17% Hispanic or Latina and 83% Non-Hispanic or Latina. For males, the overall racial distribution will be 48% White, 28% African American, 2% Asian, 4% American Indian or Alaska Native, and 18% other. The overall ethnic distribution for men will be approximately 24% Hispanic or Latino and 76% Non-Hispanic or Latino.

If the minority distribution of our participants falls below the targeted minority distribution (i.e., if

halfway through the study, the proportions of African Americans or Hispanics recruited are less than two thirds of the proportion of that minority distribution for the [REDACTED], then we will conduct additional outreach to the group that fell below their targeted enrollment numbers. We will also attempt to obtain feedback on why individuals for that group may refuse to participate in the study. Based on the feedback, we will take corrective action. All subjects will be asked to identify their race and ethnicity separately, by self-report, at the time of study entry, when demographic information is collected. We plan to conduct analysis to determine whether minority status is associated with any of the treatment utilization or clinical outcome data collected as part of this investigation.

### **3.c.2. Inclusion of Children**

Individuals aged 18-21 who meet our inclusion criteria will be included in this study. Individuals younger than 18 will not be included. This study includes children 18-21, but does not include anyone under 18 years of age (the age of emancipation in [REDACTED]) because adolescent developmental issues would confound outcomes of interest to the study. Additional instruments and study methods would also be required to assess the unique mental health needs of a younger population. Thus, the current research is not applicable to children under the age of 18.

Because children ages 18-21 are of legal age, they will be treated as adults and will be able to consent and agree to participate in the study themselves. Our consent procedures are conducted face-to-face, with trained interviewers guiding eligible subjects step-by-step; materials are written at a Grade 7 level and the interviewers ensure that each element is understood. In addition, consent forms will be read aloud.

### **3.c.3. Potential Risks**

There are three major sources of low to moderate risk associated with participation in the proposed study.

1. Potential coercion. It is possible that individuals may feel coerced into participating. This is a particularly important risk to minimize with incarcerated individuals.
2. Increased distress due to assessment or intervention procedures. It is possible that some participants will experience increased intrapersonal or interpersonal psychological distress as a result of participating in assessment or intervention. In the vast majority of cases, we believe that any increased distress experiences will be mild and transitory in nature.
3. Confidentiality and loss of privacy. The greatest potential risks to those participating in the research are legal or social, caused by the inadvertent loss of confidential information obtained during the data collection process. That is, a participant's identity may be inadvertently exposed or questionnaire material may be released or disclosed to unauthorized persons. In the case of such a breach, serious personal and social consequences could conceivably occur. However, such risks can be minimized by instituting the proper procedures to protect confidentiality and by having resources in place to provide counseling and referrals. We have extensive experience taking appropriate measures to safeguard confidential information in research with criminal justice populations. These measures are described below.

### **3.c.4. Protection Against Risks**

All aspects of the study will be conducted in accordance with HIPAA regulations. Data and safety monitoring will take place to assure the safety of subjects (see below). All participants will be reminded that their participation is voluntary and that they can withdraw at any time without penalty. Additionally, the risks described above will be minimized by the following procedures:

1. We will minimize the risk of potential coercion by following standard procedures for obtaining informed consent (please see section 3.b.5). We will begin this process during the intake where we will clarify the nature of the study and possible alternatives upfront. Prior to enrolling participants in the research, we will fully explain the study procedures, risks, benefits, and alternatives to participants,

emphasizing that participation has no impact on the other services they receive at the prison, the terms or length of their confinement, or any other community services that they receive post-release. Also, participants who do not consent or who withdraw will receive appropriate referrals (e.g., for mental health treatment), if needed. All participants will be reminded that there is no penalty for participants who choose to not participate or to withdraw from the study. All reimbursements for participating will be commensurate with participants' time required for participating in the research.

2. We will minimize the risk of distress. Incarcerated individuals with BD who serve as participants in this research face the risk of increased distress during assessment procedures or study intervention. All participants will be informed that they do not have to answer questions that they find too distressing and will be reminded that they can discontinue participation at any time. Moreover, clinical backup will be provided during all assessments and intervention sessions by a licensed clinician to help facilitate the stabilization and referral process for participants who decompensate during study procedures. The need for additional services will also be monitored during each clinical (assessment or intervention) contact. Participants will be formally assessed while they are in prison (intake, pre-release) and after release (1 and 6 months post-release). Incarcerated participants who report significant homicidal ideation or suicide risk, or who manifest significant manic or psychotic symptomatology, will be referred to appropriate clinical prison staff for evaluation, per [REDACTED] policy. For assessments in the community, a licensed clinician (the PI or her covering clinician) will be available at all times by cell-phone. Research staff will contact the licensed clinician if there are any safety concerns.

3. We will minimize potential risks due to loss of confidentiality of research data by having all information collected and handled by research staff, including study interventionists, trained to deal appropriately with sensitive clinical issues. All participants will be informed about the limits of confidentiality concerning suicidal intent, homicidal intent, suspected child abuse, suspected elder abuse, and prison-required mandatory reporting issues (i.e., sexual contact within the prison, weapons in the prison, prison escape plans). All information will be treated as confidential material and will be available only to research staff. All information will be kept in locked file cabinets at [REDACTED]. Computer data files will be kept on [REDACTED] secure research servers, will be available only to authorized personnel, and no names or obvious identifying information will be stored in data files. No participant will be identified in any report of the project. Written consent will be obtained to contact other persons for the purpose of locating the participant for follow-up and participants can refuse or revoke such requests. Participants will update their contact information and contact person for the post-release period at each assessment point to ensure that this information remains appropriate. To further protect participants, a **Federal Certificate of Confidentiality** will be granted by the NIH at the time of the Notice of Grant Award. Potential subjects will be informed that a Certificate of Confidentiality has been obtained for this project and that this certificate will protect the investigators from being forced to release any research data in which participants can be identified, even under court order or subpoena, although this protection is not absolute. Potential participants will be informed of the situations in which they may not be protected under the Certificate of Confidentiality. No information about participants will be released without their permission or where required by law.

Audio recording is necessary to rate reliability of the interview assessments and also study interventionists' fidelity to the treatment. As in our past 10 years of prison research, audio recording is accomplished through the use of credit-card size digital audio recorders, which have password-protection and encryption capabilities thereby protecting their contents during transport between the [REDACTED] and our research offices. These digital recordings are regularly transferred to [REDACTED] secure computer server (designed to hold and protect digital audio and video recordings for clinical trials) via USB connection and secure file transfer to [REDACTED] secure audio server, and the recorders are wiped. This is the same procedure that has been used in our completed and ongoing intervention studies with prisoners and jail detainees at the recruitment site. Participants will be asked to give informed written consent to audio recording at the time of intervention study entry. To assure the confidentiality and protection of participants with respect to audio taping, the following steps will be taken: a) each recording will be labeled with the participant's study identification number, the intervention

provider's/interviewer's name, and the session/interview date; b) all recordings will be stored on a secured computer server designed to hold and protect research data; and c) access to the audio recordings will be limited to research staff who need access to the recordings to perform their duties.

